Study Title	A study of the Safety, Efficacy, Longitudinal Costs and Patient Centered Outcomes using a TAAA Debranching Device
Sponsor-Investigator	[name]
NCT Number	NCT03637374
Document Description	Study Protocol and Statistical Analysis Plan
Document Date	30-Jun-20

JHM IRB - eForm A – Protocol Version 5.0

A study of the Safety, Efficacy, Longitudinal Costs and Patient-Centered Outcomes using a TAAA Debranching Device

1. Abstract

- a. Provide no more than a one page research abstract briefly stating the problem, the research hypothesis, and the importance of the research.

This study seeks to define longitudinal one year costs of delivery of care for patients who undergo care for complex aortic aneurysm disease. While surgery remains a standard treatment for complex abdominal and thoracoabdominal aneurysms (TAAA), the tolerance of the older patient to recover such extensive and brutally invasive open aortic reconstructions is poor. Endovascular may offer the opportunity to reduce patient risk with less invasive approaches, improve quality of life, and serve to reduce the cost burden to payors which encumbers such difficult surgeries. In this study, we will compare the one year costs of inpatient and outpatient care associated with complex aortic repairs, comparing both the open surgical and endovascular approach with a TAAA debranching technology to solve this difficult clinical scenario, in our hospital wherein we have established expertise in management of patients with aortic diseases and its protean manifestations.

The results of this study will serve to identify safety endpoints of endovascular technology of a TAAA debranching system, provide transparent data concerning both inpatient and outpatient costs of open and endovascular surgery in the older patient group, and patient perceptions about their care and its impact on their quality of life. Commensurate with goals of the Affordable Care Act provisions to examine clinical effectiveness and cost containment, this study may form the basis for refinement of technology used in aortic care which can motivate episode-based payment methods and further develop proper risk adjustment assessments for open and endovascular surgery considerations in the future.

2. Objectives (include all primary and secondary objectives)

Primary

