The primary safety endpoint is freedom from major adverse events (MAE) at 30 days or during hospitalization if this exceeds 30 days. Major adverse events include death, bowel ischemia, myocardial infarction, paraplegia, renal failure, respiratory failure, and stroke.

The primary effectiveness endpoint is the proportion of study subjects with treatment success at 1 year. Treatment success is defined as a composite of technical success and freedom from the following:

- Aneurysm enlargement i.e., >5mm as compared to any previous CT measure using orthogonal (i.e., perpendicular to the centerline) measurements
- Aneurysm rupture
- Aneurysm-related mortality
- Conversion to open repair

- Secondary intervention for migration, Type I and III endoleaks, device integrity failure (e.g., fracture), and patency-related events (i.e., device component stenosis or occlusion and embolic events)

The primary non-technical endpoint is improvement in quality-of-life scores (by SF36) and reduced 1 year costs for patients who undergo endovascular repair vs open surgery. **Secondary**

Secondary endpoints include:

- Technical success and the individual components of technical success:
 - Successful delivery
 - Deployment at the intended implantation site
 - Patency of all endovascular graft and stent components
 - Absence of device deformations requiring unplanned placement of an additional device
 - Absence of inadvertent covering of aortic branch vessels
 - Successful withdrawal
- Freedom from the individual components of the primary safety endpoint at 30 days.
 - Death
 - Bowel ischemia
 - Myocardial infarction
 - Paraplegia
 - Renal failure
 - Respiratory failure
 - Stroke
- Freedom from paraparesis at 30 days
- Treatment success and the individual components of treatment success including freedom from the following at each follow-up interval:
 - Aneurysm enlargement
 - Aneurysm-related mortality
 - Aneurysm rupture
 - Conversion to open repair
 - Secondary intervention for:
 - Migration
 - Type I endoleak
 - Type III endoleak
 - Device integrity failure (e.g., fracture)
 - Patency-related events (i.e., device stenosis or occlusion and embolic events)
 - Renal failure
 - All-cause mortality
 - Endoleaks
 - Device integrity failure (e.g., fracture)
 - Patency –related events (i.e., endovascular graft or stent component stenosis or occlusion and embolic events)
 - Other device-related events

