The primary technical safety endpoint is freedom from major adverse events (MAE) at 30 days or during hospitalization if this exceeds 30 days. Major adverse events include all-cause mortality within 30 days of the procedure, bowel ischemia, myocardial infarction, paraplegia, renal failure, respiratory failure, and stroke.

The primary effectiveness endpoint is the proportion of study subjects with treatment success at 1 year. Treatment success is defined as a composite of technical success and freedom from the following:

- Aneurysm enlargement i.e., ≥ 5 mm as compared to any previous CT measure using orthogonal (i.e., perpendicular to the centerline) measurements
- Aneurysm rupture
- Aneurysm-related mortality
- Conversion to open repair
- Secondary intervention for migration, Type I and III endoleaks, device integrity failure (e.g., fracture), and patency-related events (i.e., device component stenosis or occlusion and embolic events)

The primary non-technical endpoint is improvement in quality-of-life scores (by SF36) and reduced 1 year costs for patients who undergo endovascular repair vs open surgery.

B. Secondary outcome variables.

Secondary endpoints include:

- Technical success and the individual components of technical success:

- Successful delivery
- Deployment at the intended implantation site
- Patency of all endovascular graft and stent components
- Absence of device deformations requiring unplanned placement of an additional device
- Absence of inadvertent covering of aortic branch vessels
- Successful withdrawal
- Freedom from the individual components of the primary safety endpoint at 30 days.
 - Death
 - Bowel ischemia
 - Myocardial infarction
 - Paraplegia
 - Renal failure
 - Respiratory failure
 - Stroke
- Freedom from paraparesis at 30 days
- Treatment success and freedom from the following at each follow-up interval:
 - Aneurysm enlargement
 - Aneurysm-related mortality
 - Aneurysm rupture
 - Conversion to open repair
 - Secondary intervention for:
 - Migration
 - Type I endoleak
 - Type III endoleak
 - Device integrity failure (e.g., fracture)
 - Patency-related events (i.e., device stenosis or occlusion and embolic events)
 - Renal failure
 - All-cause mortality
 - Endoleaks
 - Device integrity failure (e.g., fracture)
 - Patency –related events (i.e., endovascular graft or stent component stenosis or occlusion and embolic events)
 - Other device-related events

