The primary purpose of this study is to evaluate the safety of this device as there are no or very limited devices and clinical options available for this patient population. The primary safety endpoint of this study is freedom from major adverse events (MAE) at 30 days or during hospitalization if this exceeds 30 days. Major adverse events include death, bowel ischemia, myocardial infarction, paraplegia, renal failure, respiratory failure, and stroke. The primary safety endpoint will be analyzed to determine statistical significance when compared to a target performance goal. A literature review of outcomes of open surgical repair was used to create the performance goal as there is not a comparable endovascular option to use for analysis. The performance goal was selected based on the range of subjects experiencing a major adverse event at 30 days. The range was calculated based on assumptions of the minimum and maximum number of subjects experiencing at least one MAE in the historical open surgical repair group (Table 6). Based on the literature reviewed and the above assumptions the range of subjects experiencing at least one MAE in the open surgical repair group is 30.5% to 77.4%.

The primary effectiveness endpoint is the proportion of the study subjects with treatment success at 1 year. Similarly, the data will be presented as quality outcomes with the number of study subjects with treatment success compared to the overall patient population.

The primary non-technical endpoint is patient quality of life domains at one year by SF36 testing at one year, and other follow-up intervals.

Additionally, data outcomes from this study will be entered into a common vascular database so that data can be pooled with other PS-IDEs. This would provide consistent reporting across the PS-IDEs. Additionally, the PS-IDEs will be evaluating the same device and endpoints to allow for a pool-ability of data across the sites. The data will be separated into two separate study arms: primary study arm and expanded selection arm. The primary cost related outcomes are total, global healthcare costs from time of surgery to one year after treatment with the Valiant Thoracoabdominal Stent Graft System.

Statistical Methods

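### One-year cost against open surgery is a primary endpoint, but no open cohort is specified, the stated 20 per group is not met by 16 device patients, and the 20 cannot be reproduced from the printed inputs

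*Combined protocol and SAP*

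**What the plan says.** All references are to the combined protocol and SAP.

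- **The endpoint.** Sections 2 (Objectives) and 7.A give the primary non-technical endpoint as "improvement in quality-of-life scores (by SF36) and reduced 1 year costs for patients who undergo endovascular repair vs open surgery". Grammatically, the reference to open surgery may govern cost alone or SF-36 as well.
- **The comparison as an aim.** The Abstract says the study will compare one-year costs, "comparing both the open surgical and endovascular approach with a TAAA debranching technology", and places this "in our hospital wherein we have established expertise in management of patients with aortic diseases". The Report of Prior Investigations Synopsis (section 3) and Sample Size Justification (7.C) also refer to a comparison with open repair.
- **Who is enrolled.** Study Type and Duration (4.a) enrols 16 patients, 10 in the primary arm and 6 in the expanded arm, all for treatment with the device.
- **The analysis.** Data Presentation and Analysis Plan (7.C) states: "The primary non-technical endpoint is patient quality of life domains at one year by SF36 testing at one year", with other follow-up intervals added and no comparator named. Cost is total, "global healthcare costs from time of surgery to one year after treatment with the Valiant Thoracoabdominal Stent Graft System". On arms, "The data will be separated into two separate study arms: primary study arm and expanded selection arm". Statistical Methods tests only the 30-day major adverse event (MAE) rate.
- **The size.** The cost paragraph in section 3 and Sample Size Justification in 7.C both take open one-year cost as about $150,000 plus or minus $10,000. With 80% power and alpha 0.05, they ask for 20 per group to detect $20,000. The 7.C section also limits the study to 16 patients. It adds that global one-year costs cannot be had from the literature.
- **SF-36 timing.** Purpose (section 3) has it at treatment and at each follow-up; Follow-up Visits (4.a) lists it. The screening and pre-operative lists in 4.a do not.

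**The concern.** A claim of lower cost than open surgery needs open-surgery costs, and the plan specifies how to obtain costs on the device side only. If the open group is assembled after device costs are known, the answer depends on which open patients are picked, over which years, and on how their post-discharge care is captured.

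Even a group fixed in advance would differ at baseline. Section 5 excludes good candidates who elect open repair, and section 6 says many patients with this disease are not candidates for it. No adjustment is described.

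The sample size statement adds a second difficulty. It gives a requirement of 20 per group that the same section does not meet on the device side, and it does not give enough information to judge whether that matters.

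Finally, if improvement in SF-36 means change within patients, a score before treatment is needed, and the operational lists do not schedule one.

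**Working it through.** **Step 1. What is specified for each side of the cost comparison**

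| Item | Device | Open |
|---|---|---|
| Number | 16 enrolled (10 + 6) | 20 required; none enrolled |
| Source, period, eligibility | Sections 4 and 5 | Own hospital (Abstract); nothing further |
| Cost window | Surgery to one year (7.C) | Not given |
| Cost collection | Components listed in 7.C | No method or source |
| Adjustment, named test | None | None |

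The plan does give a required open number and a target difference in means. It does not say how open patients or their costs are to be obtained.

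**Step 2. Try to reproduce 20 per group**

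Inputs printed in section 3 and 7.C: difference δ = $20,000, alpha 0.05, power 80%, spread $10,000. Assumption: the spread is a common SD σ.

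Normal approximation: n = 2(z_alpha + z_power)²(σ/δ)².

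- Two-sided: 2 × (1.960 + 0.842)² × 0.5² = 3.92, so 4 per group.
- One-sided: 2 × (1.645 + 0.842)² × 0.5² = 3.09, so 4 per group.

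Two-sample t-test (noncentral t, equal variances, δ/σ = 2):

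- Two-sided: power 0.791 at 5 per group and 0.876 at 6, so 6.
- One-sided: power 0.645 at 3 and 0.802 at 4, so 4.

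Raising power to 95% (two-sided) gives only 8. The stated 20 is not reproduced on this reading.

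**Step 3. Work back from 20 per group**

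At 20 v 20 and 80% power, the t-test detects a standardised difference of 0.909 two-sided or 0.801 one-sided. The implied SD is therefore:

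- 20,000 / 0.909 ≈ $22,000 two-sided
- 20,000 / 0.801 ≈ $25,000 one-sided

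Neither value is printed.

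**Step 4. Could the $10,000 be something other than an SD?**

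If it is a 95% CI half-width from a source of m patients, SD = 10,000 × √m / multiplier.

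- m = 18, multiplier 1.96: SD ≈ $21,600, t-test n = 20 per group.
- m = 21, multiplier 2.086 (t, 20 df): SD ≈ $22,000, t-test n = 20 per group.

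So a source of about 18 to 21 patients would give exactly 20. If it is a standard error, a source of about 5 would be needed (SD ≈ $22,400; 20 per group by the normal formula). The documents do not give the source's sample size.

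**Step 5. What 16 device patients give**

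Assumptions: 20 open patients, difference $20,000, alpha 0.05, equal SDs, complete one-year data, roughly normal costs.

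| SD | Power, two-sided | Power, one-sided |
|---|---|---|
| $10,000 | >99.9% | >99.9% |
| $15,000 | 97% | 99% |
| $22,000 | 75% | 84% |
| $25,000 | 64% | 76% |

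Power falls below 80% once the SD exceeds about $20,700 two-sided or $23,500 one-sided. The two-sided difference detectable at 80% power is 0.967 SD: about $9,700 at an SD of $10,000 and $21,300 at $22,000.

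**Step 6. Precision without a comparator**

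The 95% t half-width for a mean is 0.53, 0.72 and 1.05 SD for 16, 10 and 6 patients. At an SD of $22,000 that is about $11,700, $15,700 and $23,100.

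**The case against.** **The analysis plan is shorter, not contradictory.** The Abstract, Objectives, Synopsis, 7.A and Sample Size Justification all announce a comparison. Data Presentation and Analysis Plan omits the comparator but never calls the endpoint descriptive, and its sentence on two arms sits in the paragraph on pooling with other sites. This stands. A reader might infer that the comparison was dropped, but the text shows an incomplete specification.

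**Part of the open side is given.** A required 20 and a target mean difference are stated. This stands too, but a required number is not a cohort.

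**The 20 may be right.** A reader might infer an arithmetic error. Step 4 shows a confidence-interval reading that yields 20, so the documents support only that the figure is unsupported as printed.

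**Power may be ample.** A reader might infer that the cost comparison is underpowered. On the SD reading, 20 is more than enough and so is 16. The shortfall appears only near or above the back-solved SD.

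**Pooling could raise the device number above 20.** Possibly, if cost is pooled: Sample Size Justification names only safety and effectiveness data, while the later section is broader. Either way, pooling adds device patients only.

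**The follow-up table may be damaged.** As supplied it has no SF-36 row at all, although Follow-up Visits requires the survey, so its silence on baseline is weak evidence. A reader might infer that no baseline is intended; Purpose says otherwise. What remains is the survey's absence from the screening and pre-operative lists.

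**Conclusion.** The point holds as an incomplete specification of a labelled primary endpoint. One-year cost against open surgery (and possibly SF-36) cannot be analysed from the data the plan provides for, because no open cohort is specified beyond a required number and the investigators' own hospital.

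The section's own requirement of 20 per group is not met on the device side: 16 is 4 short. Whether this costs power is unknown. With an assumed 20 open patients, two-sided power is above 99.9% if the SD is $10,000 and 75% if it is $22,000. The $22,000 and $25,000 values are back-solved from the 20; they are not in the documents.

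The limits are clear. The 30-day MAE hypothesis is not touched, and 7.C says "The primary purpose of this study is to evaluate the safety of this device". The documents do not show that the 20 is wrong, that the comparison is underpowered, or that the sponsor abandoned it.

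**What to change.** 1. **Sample size text (cost paragraph in section 3, and 7.C).** Say what the plus or minus $10,000 is. State the SD, the sidedness and the resulting n. Replace the implied 80% power at 20 per group with the power or detectable difference for 16 device patients over a stated range of SDs, as in Step 5. This is wording only.

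2. **Endpoint (sections 2, 7.A and 7.C).** Make the three agree, and say whether the open-surgery comparison covers SF-36. Then choose one:
   - *Keep the comparison.* Before device costs are examined, fix the open cohort's source, period, number, eligibility and one-year cost including post-discharge care. Name the test, and describe any adjustment or state that there is none. Label the comparison non-randomised and exploratory. This preserves the Abstract's main aim, but needs one-year cost data on open patients (and SF-36, if compared), which nothing in the plan now provides for.
   - *If no such cohort will be assembled,* report cost and SF-36 for device patients by arm with 95% confidence intervals, and make no claim against open surgery. This needs no extra patients but gives up that aim, so the Abstract, Synopsis and Sample Size Justification must be aligned.

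3. **SF-36 baseline (4.a).** Add the survey to the screening or pre-operative assessments, in line with Purpose in section 3, so that improvement has a reference point. The cost is one questionnaire per patient.

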The primary hypothesis of the Visceral Manifold Study is the number of subjects experiencing a major adverse event through 30 days will be less than a target performance goal (PG) of 50%. The PG was determined by using a conservative target that is approximately the average of the open surgical repair MAE rate calculated above (30.5%-77.4%, Table 6). The anticipated test device 30 day MAE rate was based on the current rate of MAE's (26%, Table 7) observed in 20 subjects meeting inclusion criteria into the primary study as of June 2016.

The sample size for the Visceral Manifold Study was determined using an exact method based on a one-sided 2.5% significance level and an anticipated 26% investigational device 30 day major adverse event rate. Based on these assumptions, a sample size from the pooled PS-IDE data of 46 subjects provides at least 80% power to test the primary hypothesis.

Table 6. Historical Comparison for Primary Safety Endpoint (MAE Rate at 30 days for Open Repair)

Reference	# of Patients	Mortality	Bowel Ischemia	Myocardial Infarction	Paraplegia	Renal Failure	Respiratory Failure	Stroke
Rigberg et al	1010	191 (19%)						
Becquemin et al	1678	90 (5.4%)	51 (3%)	20 (1.2%)	16 (1%)	289 (17.2%)	124 (7.4%)	12 (0.7%)
Murana et al	542	46 (8.5%)			22 (4.2%)			
Ferrer et al	257	16 (6.2%)			53 (20.8%)	31 (12.3%)	31 (12.3%)	
Bensley et al	450	45 (10%)		10 (2.4%)		48 (10.7%)	202 (45.1%)	9 (2.2%)
Nathan et al	83	6 (5.6%)						
Dayama et al	682	68 (10%)		87 (12.9%)		117 (17.2%)	286 (42%)	
Ferrante et al	200	5 (2.5%)		25 (12.8%)		22 (11%)	27 (13.8%)	
Tsilimparis et al	1091	58 (5.4%)		87 (8%)		109 (10%)	229 (21%)	
Piazza et al	7833	1331 (17%)			587 (7.5%)	1488 (19%)	2819 (36%)	
Total	13826	1855/13826	51/1678	229/4101	678/10310	2104/12191	3718/12191	21/2128
Rate of MAE at 30 Days for Open Surgical Repair		13.4%	3.0%	5.6%	6.6%	17.3%	30.5%	1.0%

Table 7. Historical Comparison for Expected Investigational Device 30 Day MAE Rate (Outcomes of subjects treated with the Visceral Manifold System and meeting inclusion into the primary study as of June 2016)

Dataset	Mortality	Bowel Ischemia	Myocardial Infarction	Paraplegia	Renal Failure	Respiratory Failure	Stroke
Subjects meeting VMS PS-IDE I/E criteria	0/20 (0%)	0/20 (0%)	0/20 (0%)	2/20 (9.5%)	1/20 (5%)	3/20 (14%)	0/20 (0%)

Limitations of the Study

Limitations of the study are that it is a single center study with a small patient population.

Risk Analysis

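### The anticipated 26% MAE rate does not follow from Table 7, which allows 15% to 30%; 46 pooled subjects miss 80% power only at the top of that range

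*Combined protocol and SAP*

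**What the plan says.** Section 7.C, Statistical Methods, states the primary hypothesis as "the number of subjects experiencing a major adverse event through 30 days" being "less than a target performance goal (PG) of 50" per cent. The sample size was "determined using an exact method based on a one-sided 2.5% significance level" together with "an anticipated 26% investigational device 30 day major adverse event rate". The source given for that rate is "26%, Table 7) observed in 20 subjects meeting inclusion criteria into the primary study as of June 2016". The conclusion drawn is that "a sample size from the pooled PS-IDE data of 46 subjects provides at least 80% power to test the primary hypothesis".

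Table 7 has one row, with seven component events over 20 subjects: paraplegia 2 (printed as 9.5%), renal failure 1 (5%), respiratory failure 3 (14%), and zero for the other four. It has no column for subjects with one or more MAEs and says nothing about events shared by the same subject.

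For the open-repair comparator, Data Presentation and Analysis Plan in the same section does address shared events: "The range was calculated based on assumptions of the minimum and maximum number of subjects experiencing at least one MAE". That range is 30.5% to 77.4%.

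**The concern.** The endpoint counts subjects, while Table 7 counts events. A subject with both paraplegia and respiratory failure adds two events but only one failure. Without the overlap, the table cannot yield the rate it is cited for. The figure quoted is not a possible fraction of 20, and the table's own percentages do not all agree with its fractions.

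The 26% is the only device-side input to the power statement for the primary safety hypothesis. If the true subject count is low, 46 is ample. If it is at the maximum the table allows, 46 falls short of the power claimed. A reader cannot tell which applies.

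**Working it through.** **Inputs** (all from section 7.C): null MAE rate 50%; exact test, one-sided 2.5%; anticipated rate 26%; n = 46 pooled; Table 7 counts 2, 1 and 3 out of 20. No dropout is stated for the 46, and none is used here.

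**1. Reproduce the plan's figure.** Let X be the number of the 46 subjects with an MAE. Reject when X ≤ c, where c is the largest value with P(X ≤ c | p = 0.50) ≤ 0.025.
- P(X ≤ 15) = 0.0129 and P(X ≤ 16) = 0.0270, so c = 15 and the true alpha is 0.0129.
- Power at 26% is P(X ≤ 15 | p = 0.26) = 88.1%. The claim of at least 80% holds at the stated rate.

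**2. Can 26% come from 20 subjects?** 0.26 × 20 = 5.2, which is not a whole number. The neighbouring fractions are 5/20 = 25% and 6/20 = 30%.

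**3. Check the printed percentages.**

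| Event | Count | Printed | Over 20 | Over 21 |
|---|---|---|---|---|
| Paraplegia | 2 | 9.5% | 10.0% | 9.5% |
| Renal failure | 1 | 5% | 5.0% | 4.8% |
| Respiratory failure | 3 | 14% | 15.0% | 14.3% |

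The first and third match 21; the second fits either denominator after rounding. With 21 subjects the nearest fractions to 26% are 5/21 = 23.8% and 6/21 = 28.6%, so 21 does not explain it.

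**4. Apply the plan's own overlap method to Table 7.** In Table 6 the lower limit is the largest component (30.5%) and the upper limit is the sum of all seven: 13.4 + 3.0 + 5.6 + 6.6 + 17.3 + 30.5 + 1.0 = 77.4%. For the device:
- minimum (full overlap): largest component, 3/20 = 15%;
- maximum (no overlap): 2 + 1 + 3 = 6, 6/20 = 30%.

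With 21 subjects the limits are 14.3% and 28.6%. The stated 26% lies inside both ranges. It is not an end of either, nor the midpoint over 20, (15 + 30)/2 = 22.5%, nor the sum of the printed percentages, 9.5 + 5 + 14 = 28.5%.

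**5. Power of n = 46 at each rate**, P(X ≤ 15 | p):

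| Rate | Power |
|---|---|
| 3/20 = 15% | 99.9% |
| 4/20 = 20% | 98.6% |
| 5/21 = 23.8% | 93.8% |
| 5/20 = 25% | 91.0% |
| 26% (stated) | 88.1% |
| 6/21 = 28.6% | 78.2% |
| 6/20 = 30% | 71.3% |

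Power equals 80% at a true rate of 28.2%.

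**6. Sample size if the recount were 6/20.** At 30%, exact power is 74.9% at n = 48, 81.0% at 49, 78.4% at 53 and 83.7% at 54. Because exact power moves in a saw-tooth, 49 is the first n to reach 80%; every n checked from 54 to 149 stays at or above 80%.

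**7. Precision of the source data.** The exact 95% interval is 3% to 38% for 3/20 and 12% to 54% for 6/20.

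**The case against.** The strongest reply is that an anticipated rate is a planning assumption. The plan says it was based on the observed rate, and a planner may choose 26%. It sits above three of the four rates possible with 20 subjects, so it is cautious in three cases out of four, and the power claim is correct at that value. With 21 subjects the worst case is 78.2%, less than two points short. Sampling error in 20 subjects is far larger than the gap between 25%, 26% and 30%. And 46 belongs to the pooled data across the physician-sponsored studies; this site's 16 patients are justified as preliminary safety data, not by power.

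Most of this stands, and it limits the point. No underpowering is shown, and nothing in this site's enrolment depends on it. It does not remove the error: the plan does not offer 26% as a judgement but reports it as observed in 20 subjects and cites a table that cannot produce it. A rate among a different number of evaluable subjects could round to 26% (5/19 = 26.3%, 6/23 = 26.1%), but neither denominator appears in the document. The wide intervals are a reason to show power over a range, not to leave the input unexplained.

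**Conclusion.** The point holds. As a simple proportion, 26% is not attainable with 20 subjects or with 21. Table 7 omits the quantity the hypothesis is about, and two of its percentages disagree with their printed fractions. Its counts bound the device rate at 15% to 30% (14.3% to 28.6% if the denominator is 21). Over that range the power of 46 subjects runs from 99.9% down to 71.3% (78.2% for 6/21), and it is below 80% only with no overlap at all, that is, six affected subjects.

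This assumes the printed counts are right and that each event belongs to a subject in the stated group. It should be fixed: the error in the input is definite, while the effect on power is uncertain and may be nil.

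**What to change.** - Recount the subjects with at least one MAE and add that count to Table 7.
- Settle the denominator (20 or 21) and correct the printed percentages.
- Replace 26% with the resulting fraction, or state how 26% was derived.
- Restate the power of 46 pooled subjects at that rate. If the overlap cannot be recovered, show power over 15% to 30%.

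A related clarification can go in at the same time. Data Presentation and Analysis Plan says "The primary safety endpoint will be analyzed to determine statistical significance when compared to a target performance goal" without saying on which data. State that this is the pooled primary-arm test described under Statistical Methods, and that this site's 10 primary-arm patients are reported with an exact confidence interval. A test on those 10 alone would reject only at 1 or fewer MAEs and would have 22% power at 26%.

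The cost is one recount and some wording. Enrolment of 16 at this site and the 50% goal stay as they are. The pooled 46 needs another look only if the recount is six subjects.
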